3.3.2.2. Anti-fXa Activity

Anti-fXa activity was chosen as the most relevant pharmacodynamic (PD) marker to evaluate the biochemical reversal of anticoagulation based on several mechanistic and empiric observations:

- In Phase 2 dose ranging trials with rivaroxaban and apixaban in patients who had undergone total knee replacement surgery or had symptomatic acute venous thrombosis, increasing the dose of the anticoagulant correlated with increased plasma drug concentration and increased frequency and severity of bleeding [15, 16].
- Plasma concentration of a FXa inhibitor correlates well with *ex vivo* anti-fXa activity [17, 18].
- The unbound plasma concentration of apixaban but not total plasma concentration correlates with anti-fXa activity in patients treated with andexanet in Study 12-502.
- Only the free, unbound plasma fraction of FXa inhibitor appears to account for the anticoagulant effects of the FXa inhibitors based on a critical level below which antifXa activity is lost [19-21].
- In animal models of blood loss, decrease in the plasma free fraction of FXa inhibitor and/or anti-fXa activity correlates with reduction in blood loss [15, 22].
• In patients with intracerebral bleeding while anticoagulated with FXa inhibitors, there was a strong positive association between baseline anti-fXa activity and the later occurrence of hematoma expansion [8].

3.3.3. Rationale for the Dose Regimen of Andexanet

Patients will receive one of two doses of andexanet based on the specific anticoagulant taken and timing of the last dose.

The and exanet dosing regimens to be examined in this study are as follows:

- Low dose: 400 mg IV bolus followed by a continuous infusion of 480 mg at 4 mg/min.
- High dose: 800 mg IV bolus followed by a continuous infusion of 960 mg at 8 mg/min.

The continuous infusion will last approximately 120 minutes for all patients. A dosing schema, categorized by FXa inhibitor and time from last dose, is provided in Table 4.

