10.5.4.2. Primary Efficacy Endpoint Analysis

The primary objective of the study is to compare the proportion of patients with effective hemostasis (excellent or good as adjudicated by the blinded EAC) between and exanet and usual care. The following hypothesis will be evaluated:

Ho: $\pi_{UC} - \pi_{andexanet} = 0$ HA: $\pi_{UC} - \pi_{andexanet} \neq 0$

Analysis will be performed using a Cochran-Mantel Haenszel (CMH) test stratified by time from symptom onset to baseline imaging scan (< 180 minutes vs. \geq 180 minutes). The corresponding 95% confidence intervals (CIs) for the difference in proportions, and the proportions from the two groups, will be provided.

The study will be considered to meet its primary efficacy objective if the proportion of and exanet-treated patients with effective hemostasis (excellent or good as adjudicated by the independent EAC) is significantly higher (p < 0.031 at the interim analysis, OR p<0.0277 at the final analysis) than the proportion of patients with effective hemostasis randomized to usual care.

A sensitivity analysis will be performed using a CMH test stratified by intended-usual-care-agent and time from symptom onset to baseline imaging scan.

Further details of the primary analysis will be provided in the SAP.

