10.8. Subgroup Analyses

Subgroup analyses may include, but not necessary be limited to, the following parameters: baseline anti-fXa activity above and below 30 ng/mL, baseline anti-fXa activity above and below 75 ng/mL, age (less than 65, 65-74, 75 or greater), sex, race (all groups with 5 or more patients), geographical region (North America, Europe, Asia), FXa inhibitor at randomization, indication for FXa inhibitor (atrial fibrillation, VTE, other), time at randomization since last FXa inhibitor dose (within 8 hours or more than 8 hours), andexanet dose, hematoma expansion risk as measured by baseline hematoma volume (< 30 mL, \geq 30 mL; < 0.5 mL, \geq 0.5 mL), determination of ICrH score at baseline(< 3, \geq 3), baseline intracranial bleed location, and usual care received (andexanet vs PCC, andexanet vs non-PCC).

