3. SAMPLE SIZE DETERMINATION

Results (as of 30 Jun 2020) from the Phase 3b/4, single-arm, open-label Study ANNEXA-4 have shown that the rate of effective hemostasis is 79% (95% CI: 74% to 84%) based on evaluable participants with ICrH; the rate of effective hemostasis is 80% (95% CI of 75% to 84%) based on 340 efficacy-evaluable participants with all types of bleeding.

Based on these results, it is assumed that the rate of effective hemostasis in this study is 70% and 80% for participants treated with UC and andexanet, respectively. The 10% absolute difference represents a 33% risk reduction of not achieving effective hemostasis by andexanet as compared to UC, which is considered clinically meaningful. After accounting for early discontinuation rate and one interim analysis, it is estimated that a total sample size of approximately 900 participants (ie, 450 participants per group) will have approximately 90% power to detect a 10% absolute difference between andexanet and usual care in the rate of effective hemostasis at a 0.05 two-sided overall significance level.

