5.1.1. Hypothesis Testing and Significance Level

For the interim analysis or the final analysis, a hierarchical testing procedure will be used to test the primary and secondary endpoints to control the overall family-wise type I error rate at 5%. At interim, the primary endpoint will be tested at a significance level of 0.0310; if the primary endpoint is statistically significant, the secondary endpoint will be tested at a significance level of 0.0310.

The same approach will be used in the final analysis with a significance level of 0.0277.

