5.3.2. Main Analytical Approach

Primary analysis will be performed using a CMH test stratified by time from symptom onset to the baseline imaging scan (< 180 minutes versus \geq 180 minutes). The difference in the proportion of participants with effective hemostasis, its 95% CI, and the p-value will be estimated.

A by-participant listing of effective hemostasis will be provided.

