5.9.1. Stopping Criterion Due to Efficacy at Interim

The overall type I error for the interim and final analyses is controlled at 5% by employing the alpha spending function by Lan and DeMets based on Pocock boundaries (DeMets, 1994). If the interim p-value is < 0.0310 for comparing and exanet and UC in the primary endpoint analysis, DSMB may recommend stopping the study. In this case, the efficacy results from the interim analysis (with 50% of the anticipated participants) will be used for regulatory communication and submission. Enrollment of participants will proceed without interruption while the analysis is ongoing, resulting in > 50% of the anticipated participants in the final data cutoff; efficacy analysis on the final data cutoff will be considered as a sensitivity analysis.

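### The primary CMH test adjusts only for dichotomised onset-to-scan time and leaves out baseline hematoma volume and baseline anti-fXa activity, giving up a modest amount of precision

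*SAP*

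**What the plan says.** Protocol 10.5.4.2 sets the primary test: "Analysis will be performed using a Cochran-Mantel Haenszel (CMH) test stratified by time from symptom onset to baseline imaging scan". SAP 5.3.2 repeats it: "Primary analysis will be performed using a CMH test stratified by time from symptom onset to the baseline imaging scan". Table 3 in SAP 5.3.1 ties the estimate to the same one-factor CMH. The factor has two levels, below 180 minutes and 180 minutes or more.

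Protocol 3.2.1 stratifies randomisation on that factor because it regards it as predictive of expansion. Two other baseline measurements are linked to expansion elsewhere:

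- Protocol 10.8 lists, among the subgroups, "hematoma expansion risk as measured by baseline hematoma volume".
- Protocol 3.3.2.2 cites a "strong positive association between baseline anti-fXa activity and the later occurrence of hematoma expansion".

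Appendix A of the protocol schedules the baseline scan and the central anti-fXa sample before randomisation. In SAP 5.3.3, sensitivity analyses 1 and 5 add only intended PCC use and amendment period; analyses 2 to 4 change the analysis set or the handling of missing status. Volume and anti-fXa activity appear for the primary endpoint as subgroup cuts (SAP 5.8). Baseline anti-fXa activity is a covariate in the secondary rank ANCOVA (SAP 5.4). It is also in the correlation model (SAP 5.5.7), but that model conditions on the post-randomisation fall to nadir, so it does not estimate the total treatment effect. No reason for leaving the two out of the primary analysis is given.

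**The concern.** The endpoint depends largely on whether the hematoma grows relative to baseline. If baseline volume and anti-fXa activity predict growth, a test that ignores them carries avoidable variance, and chance imbalance in them stays in the estimate. Randomisation is not stratified on either, so the analysis is the only place left to deal with that. Elsewhere the SAP does adjust for the baseline value: anti-fXa activity (5.4), ETP (5.5.1), mRS (5.5.3), NIHSS and GCS (5.5.4).

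The stake is largest at the interim, with about 225 patients per arm. Under SAP 1.2 and 5.9.1, a stop for efficacy makes that estimate the confirmatory result.

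**Working it through.** **Inputs from the documents.** Rates of 70% and 80%, 450 per arm, 1:1, "at a 0.05 two-sided overall significance level" (SAP 3). "At interim, the primary endpoint will be tested at a significance level of 0.0310" and "The same approach will be used in the final analysis with a significance level of 0.0277" (SAP 5.1.1), "employing the alpha spending function by Lan and DeMets based on Pocock boundaries" (SAP 5.9.1), with the interim at half the information. **Not given:** the discontinuation rate, and the share of outcome variance (R²) that volume and anti-fXa activity explain beyond onset time. R² is an assumption here, shown from 0.01 to 0.10.

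**Step 1: reproduce the plan.** Pocock-type spending at 50% information gives 0.0310 at the interim and a nominal 0.0277 at the end, 0.0500 overall. For power:

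- se = √((0.8×0.2 + 0.7×0.3)/450) = √(0.37/450) = 0.02867
- θ = 0.10/0.02867 = 3.487
- null se s₀ = √(2×0.75×0.25/450) = 0.02887, so s₀/se = 1.0067
- b₁ = 2.157×1.0067 = 2.172 and b₂ = 2.201×1.0067 = 2.216
- Power = 1 − P(Z₁ < b₁, Z₂ < b₂), where the means are θ√0.5 and θ and the correlation is √0.5

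The result is 90.9%. Interim power alone is Φ(3.487×0.7071 − 2.172) = Φ(0.294) = 61.6%. Treating dropout as lost sample size gives 90.0% at 3%, 89.4% at 5% and 87.7% at 10%. The plan's figure of about 90% holds.

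**Step 2: add the covariates.** Adjustment divides the variance of the risk difference by 1/(1 − R²), so θ becomes θ/√(1 − R²).

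| Assumed incremental R² | Two-look power | Gain | Interim power | Gain | Total N for 90% |
|---|---|---|---|---|---|
| 0 | 90.9% | – | 61.6% | – | 872 |
| 0.01 | 91.2% | 0.3 | 62.1% | 0.5 | 863 |
| 0.02 | 91.5% | 0.6 | 62.5% | 1.0 | 855 |
| 0.05 | 92.3% | 1.4 | 64.0% | 2.4 | 828 |
| 0.10 | 93.6% | 2.7 | 66.6% | 5.0 | 785 |

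In patients, the gain is 900×R²: 9 at 0.01, 45 at 0.05, 90 at 0.10. In precision, the 95% interval shrinks by the factor √(1 − R²). At R² = 0.10 that is 0.949: the half-width goes from 1.96×0.02867 = 5.6 points to 5.3 at the final analysis, and from 1.96×√(0.37/225) = 7.9 points to 7.5 at the interim.

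**Step 3: simulation.** The planned CMH was compared with a standardised logistic risk difference that adds the two covariates (4,000 runs per setting, 900 patients, single look at 0.0277). The simulation assumed 60% of patients in one onset stratum and an onset-time odds ratio of 1.5.

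| Odds ratio per SD (volume, anti-fXa) | CMH | Adjusted |
|---|---|---|
| 1.0, 1.0 | 90.7% | 90.7% |
| 1.25, 1.25 | 91.0% | 91.6% |
| 1.5, 1.5 | 90.4% | 92.0% |
| 2.0, 1.5 | 89.5% | 92.2% |

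At the interim size (450 patients, 0.0310), odds ratios of 1.5 and 1.5 gave 61.1% against 63.5%. Under the null, rejection was 0.023 for the CMH and 0.027 for the adjusted test, both below 0.0277. When the covariates carry no information, nothing is gained or lost.

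**The case against.** The strongest reply is that nothing is broken. The CMH is valid, type I error is controlled and the stated power is delivered. Subgroup analyses and baseline tables already look at volume and anti-fXa activity. The version history records that SAP 1.0 moved the primary analysis to one stratification factor, in a revision made partly to take in regulatory comments, so replacing the test is more than an edit. All of this stands, with two limits: subgroup cuts and balance tables recover no precision, and the version history does not mention volume or anti-fXa activity.

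On data quality, eligibility uses an estimated volume, and the core-laboratory value comes later. Central anti-fXa values can be missing (SAP 5.4) or out of stability (SAP 5.11). The core-laboratory volume is still a baseline covariate, since it comes from the baseline scan and is read blinded. The missing values need a rule.

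The cited links are to expansion. The endpoint adds NIHSS change, rescue therapy and non-evaluable cases scored as failures. The treatment is meant to remove anti-fXa activity, so that association may be weaker in the andexanet arm. Both could push the gain towards the low end.

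Three stronger readings are tempting, and the documents support none of them:

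- A reader might infer that the test ignores baseline expansion risk altogether. It does not: Protocol 3.2.1 names onset-to-scan time as predictive, and 3.3.1 puts the highest risk in the first 3 hours, which is the cut used.
- A reader might infer that the trial is underpowered. Step 1 shows otherwise for the stated assumptions.
- A reader might expect a large gain. A covariate–outcome correlation of 0.5 (R² = 0.25) would add 5.8 points (91.2% to 97.0% with the unpooled variance). Nothing in the documents supports that value; it is close to what a single covariate with an odds ratio of about 4.5 per SD (e^1.5) would give.

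**Conclusion.** The point holds as a cheap improvement. The primary test adjusts for one protocol-named predictor of expansion and leaves out two others that are scheduled before randomisation. The cost is some precision, not validity: about 0.3 to 2.7 points of two-look power and about 0.5 to 5 points at the interim, if the two covariates add an R² of 0.01 to 0.10 beyond onset time. That range is an assumption, and the true gain may lie at or below its lower end because of the composite endpoint. Baseline NIHSS is not named in the documents as a predictor of expansion; its case rests only on being the reference value for one component.

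**What to change.** Before any unblinded result is seen, amend SAP 5.3.2, SAP Table 3 and Protocol 10.5.4.2:

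- Estimate the same marginal difference in proportions by standardisation (g-computation) from a logistic model with treatment, the onset-to-scan stratum, log core-laboratory baseline volume and baseline anti-fXa activity, with a robust standard error. Baseline NIHSS is optional.
- Fix a treatment-blind rule for missing covariates: single imputation plus a missing indicator, so that the ITT set stays whole.
- Use this statistic at the interim, at the final analysis, and for Z₁ and Z₂ in the weighted test of SAP 5.9.3. Keep the stratified CMH as a sensitivity analysis.

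If the CMH is kept as primary because it has been through regulatory review, prespecify the adjusted estimate and its interval as supportive. That shows whether the result survives chance imbalance in the two predictors, but it recovers no confirmatory power.

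No new data are needed. The costs are a working model, a missing-covariate rule and an amendment to an agreed primary test. The null simulation above covered a single look, so the two-look and weighted versions should be simulated before adoption.

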5.3.3. Sensitivity Analysis

The following sensitivity analysis will be performed to evaluate the robustness of the primary efficacy results:

Sensitivity analysis 1: The same analysis for the primary endpoint described in Section 5.3.2 with 2 stratified factors in the CMH test: intended PCC use (yes versus no) and the time from symptom onset to baseline imaging assessment (< 180 minutes versus \ge 180 minutes). For this analysis, participants who do not have intended PCC use data collected will be excluded.

Sensitivity analysis 2: The same analysis for the primary endpoint described in Section 5.3.2 on the PPS.

Sensitivity analysis 3: The same analysis for the primary endpoint described in Section 5.3.2 on the ITT Set, excluding participants with nonevaluable hemostatic status due to administrative reasons.

Sensitivity analysis 4: To evaluate the impact of the missing hemostatic status due to administrative reasons, 3 statistical methods for missing data imputation will be applied on the ITT Set as follows:

Page 20 of 52 Alexion Confidential **Worst-case scenario imputation**. In this case, missing hemostatic status in the andexanet group will be imputed as poor/none, whereas missing status in the UC group will be imputed as excellent/good. The same method used in the primary analysis described in Section 5.3.1 will be used to compare andexanet and UC. This imputation represents the worst possible case for missing hemostatic status; if the statistical comparison reaches significance (p < 0.05), the following imputation methods will not be performed.

Jump-to-control imputation. This approach imputes missing hemostatic status using only data from the UC group. For a given participant with missing status, his/her status will be generated based on the probability of effective hemostasis in the UC group estimated with available data, regardless of the treatment group this participant is randomized to.

Tipping point. In this case, missing hemostatic status will be imputed over a series of scenarios to evaluate at what point the significance in andexanet and UC comparison will be overturned.

A logistic regression model will be first estimated for the effective hemostasis, with treatment group and time from symptom onset to the baseline imaging scan in the model. Then, a shift parameter δ will be applied to the log odds ratio in the logistic regression model to impute the missing data.

The shift parameter will take a series of values; for each value, the imputation will be applied to generate 100 datasets, and the same stratified CMH method as described in Section 5.3.1 will be used to compare andexanet and UC. Rubin's rule (Rubin, 1967) will be applied to combine results.

At the end of this process, a plot for the p-values with the shift parameter values will be generated to evaluate the impact of missing data imputation to the statistical comparison.

Sensitivity analysis 5: The primary endpoint will be analyzed by a CMH method with a 5-stratum stratification factor. The 5 strata are:

- Participants enrolled prior to Protocol Amendment V1 who were randomized not by stratifying intended PCC use (yes versus no)
- Participants enrolled after Protocol Amendment V1, and with intended PCC use and the time from symptom onset to baseline imaging assessment < 180 minutes
- Participants enrolled after Protocol Amendment V1, and with intended PCC use and the time from symptom onset to baseline imaging assessment ≥ 180 minutes
- Participants enrolled after Protocol Amendment V1, and with no intended PCC use and the time from symptom onset to baseline imaging assessment < 180 minutes
- Participants enrolled after Protocol Amendment V1, and with no intended PCC use and the time from symptom onset to baseline imaging assessment \geq 180 minutes

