10.1. General Considerations

During the conduct of the study, the Sponsor and Investigators will be blinded to the aggregated efficacy and safety summaries. Also, all unblinded analyses that are required to support the DSMB will be performed by an independent unblinded statistician. These analyses will be performed under the direction of the DSMB according to the Statistical Analysis Plan (SAP) and the DSMB Charter. The results of these unblinded analyses will not be available to the Sponsor or Investigators until after database lock, unless the DSMB recommends early termination of the trial.

The safety interim analyses will follow the same procedures as the efficacy interim analysis (see Section 10.7), with the Sponsor remaining blinded to the results of these analyses unless the DSMB recommends stopping the trial early.

Once the study is complete and the final database lock is performed, the study will be fully unblinded and final analyses will be performed.

All efficacy hypothesis tests will be 2-sided and performed at the 0.05 significance level. Adjustments for the overall type I error for the planned interim efficacy analysis are described in Section 10.7.

It is anticipated that statistical summaries will be performed using SAS Version 9.2 (SAS Institute, Inc., Cary, NC, USA) or higher. Additional software may be used for the production of graphics and for statistical methodology not available in SAS.

All efficacy and safety endpoint parameters will be summarized descriptively.

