2. STATISTICAL HYPOTHESES

The primary objective of this study is to compare the rate of effective hemostasis between and exanet and UC group. The following hypothesis will be evaluated:

Ho:
$$\pi_{UC} - \pi_{andexanet} = 0$$

HA: $\pi_{UC} - \pi_{andexanet} \neq 0$

where π is the rate of effective hemostasis in each group.

Comparison will be performed using a Cochran-Mantel-Haenszel (CMH) test stratified by time from symptom onset to the baseline imaging scan (< 180 minutes versus \geq 180 minutes). The difference in the proportion of participants with effective hemostasis between andexanet and UC group, the corresponding 95% confidence intervals (CIs) for the difference, and the p-value for the comparison will be provided.

The analysis of efficacy will employ an alpha spending function by Lan and DeMets based on Pocock boundaries. The primary efficacy objective of the study will be considered met if the proportion of participants with effective hemostasis in the andexanet group is statistically significantly higher than that in the UC group at interim (p < 0.0310) or in the final (p < 0.0277) analysis.

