5.3.1. Estimand

Table 3 below describes the attributes of the Primary (Composite) estimand.

Page 17 of 52 Alexion Confidential

Estimand	Attributes of Estimand				
	Treatment	Endpoint	Population	Intercurrent Events Handling	Statistical Summary
Primary (composite estimand)	Andexanet vs usual care	Proportion of participants with effective hemostasis	ITT Set	Rescue medications/procedures: All participants will be considered as poor/none (not effective) for effective hemostasis if meeting Criteria 1 and/or 2 below: 1. Initiation of rescue therapies (medication or procedures) starting ≥ 3 hours post- randomization and up to < 12 hours post-	Difference in the proportion of participants with effective hemostasis between the 2 treatment groups, and its 95% confidence interval as estimated by a CMH test stratified by the time from symptom onset to baseline imaging assessment (< 180 minutes vs ≥ 180 minutes)

Table 3:Attributes of Primary (Composite) Estimand

Estimand	Attributes o	of Estimand			
	Treatment	Endpoint	Population	Intercurrent Events Handling	Statistical Summary
				change from baseline to 12 hours in hematoma volume.	
				 Core imaging laboratory request for EAC review. 	
				4. Misadministration of procoagulant blood products contrary to treatment allocation within 3 hours pos-randomization (including andexanet in usual care arm)	
				5. Performance of a surgery or interventional procedure to treat the index hematoma or that could impact hematoma volume within 3 hours post- randomization	
				Nonevaluable events : There are 2 types of reasons for nonevaluable hemostatic status:	
				 Cases deemed nonevaluable due to administrative reasons (for example, but not limited to, follow-up scan not available, not performed not 	
				performed, not interpretable, or transfer of the participant to another facility for administrative purposes)	
				 Cases deemed nonevaluable due to clinical reasons (for example, but not 	

Table 3:Attributes of Primary (Composite) Estimand

Estimand	Attributes of Estimand					
	Treatment	Endpoint	Population	Intercurrent Events Handling	Statistical Summary	
				limited to, the participant died due to index bleed or the participant had unplanned surgery draining hematoma) The decision of the EAC is considered final. The nonevaluable status due to both reasons will be treated as poor/none in the primary analysis.		

 Table 3:
 Attributes of Primary (Composite) Estimand

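### Sensitivity analysis 4 skips jump-to-control and tipping point once the worst case gives p < 0.05, but the trial's own significance level is 0.0310 (interim) or 0.0277 (final)

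*SAP*

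**What the plan says.** For hemostatic status missing for administrative reasons, SAP 5.3.3 (Sensitivity analysis 4) states that "3 statistical methods for missing data imputation will be applied on the ITT Set as follows": worst case, jump-to-control and tipping point. In the worst case, missing andexanet patients become failures and missing usual-care patients become successes, and the primary method is re-applied. The SAP then says "if the statistical comparison reaches significance (p < 0.05), the following imputation methods will not be performed". For the tipping point, "a plot for the p-values with the shift parameter values will be generated"; no reference level is named for that plot.

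The level for the primary comparison is set elsewhere. SAP 2 counts the primary objective as met if andexanet is significantly better "at interim (p < 0.0310) or in the final (p < 0.0277) analysis". SAP 5.1.1 tests at 0.0310 at the interim and adds: "The same approach will be used in the final analysis with a significance level of 0.0277". SAP 5.9.1 ties early stopping to the same figure: "If the interim p-value is < 0.0310 for comparing". Protocol 10.5.4.2 gives the same two levels.

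SAP Table 3 fixes how these patients enter the primary analysis: "The nonevaluable status due to both reasons will be treated as poor/none in the primary analysis".

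**The concern.** The logic of skipping is sound in itself. If the conclusion survives the most hostile assignment of the missing outcomes, milder assignments need not be run. That holds only if surviving means that the primary criterion is still met. At 0.05 it does not mean that. When the worst-case p lies from 0.0310 up to 0.05 at the interim, or from 0.0277 up to 0.05 at the final analysis, the hostile assignment has removed significance as the trial defines it, and the plan treats the result as robust.

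What is lost is the evidence needed to read such a worst case. Jump-to-control shows whether a realistic unfavourable assumption also loses significance. The tipping point shows how far the assumption must move before it is lost. In this band a tipping point is known to exist, and the plan would not locate it.

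**Working it through.** **1. The plan's own levels.** Inputs: overall two-sided 0.05, Lan-DeMets spending of Pocock type, interim at 450 of 900 (SAP 1.2, 2, 3).

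- Interim: 0.05 × ln(1 + (e − 1) × 0.5) = 0.03101, z = 2.157. The SAP's 0.0310 is reproduced.
- Final: solving for a total of 0.05 with correlation √0.5 between the looks gives 0.02774, z = 2.201. The SAP's 0.0277 is reproduced.
- The skip rule uses z = 1.960. Testing at 0.05 at both looks would give an overall type I error of about 0.083, so 0.05 is not the level at which this trial calls a result significant.

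**2. What the worst case changes.** Administrative non-evaluables are already failures in both arms in the primary analysis (SAP Table 3). The worst case leaves the andexanet count as it is and moves each missing usual-care patient from failure to success. A few usual-care patients therefore decide the outcome.

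**3. Interim example** (one stratum, pooled two-proportion z test; counts are assumptions). With 225 per arm, x_A andexanet successes and x_U usual-care successes, z = [(x_A − x_U)/225] / √[p(1 − p) × 2/225], where p = (x_A + x_U)/450.

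- Primary, 176 v 152: p = 0.7289, standard error 0.0419, difference 24/225 = 0.1067, z = 2.545, p-value 0.0109. This meets 0.0310.

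| Usual-care patients missing | Worst-case comparison | z | p-value | Meets 0.0310? | Later methods run? |
|---|---|---|---|---|---|
| 3 | 176 v 155 | 2.245 | 0.0248 | yes | no |
| 4 | 176 v 156 | 2.144 | 0.0321 | **no** | **no** |
| 5 | 176 v 157 | 2.042 | 0.0412 | **no** | **no** |
| 6 | 176 v 158 | 1.940 | 0.0524 | no | yes |

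The one-stratum CMH version gives 0.0110, 0.0323 and 0.0414 for 0, 4 and 5 missing. In the two bold rows the cancelled jump-to-control would give a p-value of about 0.01 with equal missing counts in both arms, and 0.024 or 0.029 with missing in usual care only. All of these meet 0.0310.

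**4. Final-analysis example** (450 per arm, 4 missing per arm, assumed). Primary 342 v 311 gives p = 0.021, which meets 0.0277. Worst case 342 v 315 gives p = 0.043, which misses 0.0277 and still cancels the other two methods.

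**5. How often, at the interim.** Simulation of 3,000,000 interim looks per missingness rate: 225 per arm, true rates 80% and 70% with non-evaluables counted as failures, one-stratum CMH. The documents give no rate of administrative missingness, so a range is used. About 62% of trials succeed at the interim. The third column is the product of the first two.

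| Missing per arm (assumed) | Worst case misses 0.0310 but later methods cancelled, % of interim successes | Of those, jump-to-control also misses 0.0310 | Product, % of interim successes |
|---|---|---|---|
| 0.25% | 3.5 | about 41% | 1.4 |
| 0.5% | 6.4 | about 26% | 1.7 |
| 1% | 10.2 | about 10% | 1.0 |
| 2% | 12.6 | about 1% | 0.1 |
| 3% | 12.4 | about 0% | 0 |
| 5% | 9.6 | about 0% | 0 |

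Jump-to-control here imputes missing patients in both arms at the observed usual-care rate, with Rubin's total variance over 100 imputations. If the usual-care missing count is drawn independently of outcome, the first column becomes 3.5/6.4/10.0/12.3/12.0/9.3%.

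No percentage is given for the final analysis. About 75% of continuing trials fall in the 30–90% conditional-power zone, where the sample size may be raised and the final statistic changes.

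**The case against.** The best defence is that 0.05 is a deliberate nominal level. SAP 5.1.1 assigns 0.0310 and 0.0277 to the primary and secondary endpoints only, sensitivity analyses decide nothing, Protocol 10.1 names 0.05 for efficacy tests, and the reported interval is a 95% one. This does not carry the point. Protocol 10.1 continues: "Adjustments for the overall type I error for the planned interim efficacy analysis are described in" Section 10.7. Neither document sets 0.05 as a general descriptive level for sensitivity analyses or gives a reason for it here. SAP 5.3.3 says that its purpose is the robustness of the primary result, and that result is judged at 0.0310 or 0.0277. The p-value also acts here as a decision rule that removes prespecified analyses.

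The objection about weight has more force. The worst-case p-value is still produced, so a reader can see that it exceeds 0.0310, and sensitivity analysis 3 is always run. In most affected trials jump-to-control would have favoured andexanet. Hiding an unfavourable one occurs in at most about 1.7% of interim successes, or about 1% of all trials (1.7% × 0.62). That stands and limits the consequence.

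A further objection is that naming two levels leaves two cases open: the extended data set after early stopping, which has no assigned level, and the weighted statistic after a sample-size increase. These gaps are already in the SAP and do not make 0.05 right.

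**Conclusion.** The concern holds. The skip rule declares the worst-case comparison significant at a level the trial does not use for that comparison, so it can cancel jump-to-control and the tipping point when the worst case has overturned the primary conclusion. Under the planned rates and assumed administrative missingness of 0.25% to 5% per arm, this affects about 3.5% to 12.6% of trials that succeed at the interim. The usual loss is supportive context and the tipping-point display. The more serious loss, an unseen jump-to-control failure, arises mainly when missingness is about 1% or less and the primary p-value is close to the boundary.

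The defect is confined to the robustness assessment; the primary decision and type I error are not affected. The mismatch itself follows from the text alone. Its frequency depends on the missingness assumptions and on a one-stratum simplification of the stratified test. It should be corrected, and correcting it before unblinding avoids a post hoc choice about which robustness analyses to show.

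**What to change.** In SAP 5.3.3, Sensitivity analysis 4, change the skip condition from p < 0.05 to p < 0.0310 (interim) or p < 0.0277 (final) in favour of andexanet. Mark the same level on the tipping-point p-value plot, so that the point at which significance is lost is read against the trial's criterion.

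This is one line of SAP wording, with no new data and no change to the primary analysis. The only cost is that two imputations already planned are run in more cases. Deleting the condition and always running all three methods would also work; it needs no threshold for skipping and avoids the open cases noted above, but the plot would still need its reference level.
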